#### 3.1 STUDY OUTCOME MEASURES

#### Primary Outcome

a) Change in prevalence of headlice between baseline and follow-up

#### Sample Size

The required sample size was calculated to be 150 individuals based on the following assumptions.

- Pre-treatment prevalence of headice of about 25%
- Post-treatment prevalence of headlice of about 10%
- Enrolment 80%

Data and all appropriate documentation will be stored for a minimum of 5 years after the completion of the study, including the follow-up period.

#### 3.2 **RISKS AND BENEFITS**

The safety profile of ivermectin is very well known. Safety has been well studied through its usage therapeutically and in large scale MDA programs. In the past 21 years, more than 1 billion doses of ivermectin tablets have been distributed for both onchocerciasis and lymphatic filariasis. Several studies of pregnant women accidentally given ivermectin showed no evidence of teratogenicity[4–6].

Participants will benefit from receiving treatment for scabies and headlice as part of the study. These are both major public health problems in the Solomon Islands and participants will therefore gain benefit from receiving the best available treatment for these conditions which, it is believed, will result in improvements in their health and well being.

#### **Benefits to Communities**

Communities will benefit from receiving treatment for scabies as part of these studies. This is a major public health problems in the Solomon Islands and participants will therefore gain benefit from receiving the best available treatment for this condition which, it is believed, will result in improvements in their health and well being.

#### **Blinding**

This is an open-label study

# 4. SELECTION AND WITHDRAWAL OF PARTICIPANTS

# 4.1 PRE-TREATMENT EVALUATIONS

Treatment of the whole community with Ivermectin and Permethrin is the best available treatment for the purpose of scabies control. Individual treatment results in re-infestation and treatment failure. In line with recommendation therefore treatments is offered to all individuals regardless of the presence/absence of clinical features of either disease.

## 4.2 INCLUSION CRITERIA

All consenting individuals in the participating communities will be eligible to participate

## 4.3 EXCLUSION CRITERIA.

Individuals not consenting to participate in the study.

Individuals who are unwell on the day that study medications are administered.

## 4.4 WITHDRAWAL CRITERIA

Study participation is voluntary and study participants can withdraw at any time. The number of withdrawals will be recorded and only data collected prior to withdrawal will be included in the analysis. Only data collected prior to withdrawal will be included in the analysis.

# 5. TRIAL MEDICATION

# **5.1** Name and description of investigational medicinal product(s)

No investigational treatments are being tried. Ivermectin (and permethrin) is a recognised treatment for scabies and is on the Solomon Islands Essential Drug List for this indication.

## **Ivermectin**

Ivermectin is an anthelminthic. Ivermectin is metabolized in the liver, and ivermectin and/or its metabolites are excreted almost exclusively in the feces over an estimated 12 days, with less than 1% of the administered dose excreted in the urine. After oral administration, the apparent plasma half-life of ivermectin is approximately 16 hours. Ivermectin is indicated for the treatment of onchocerciasis or river blindness caused by Onchocerca volvulus and for strongyloidiasis caused by Strongyloides stercoralis. The recommended dosage for treatment of scabies is two oral doses designed to provide approximately 200µg of ivermectin per kg of body weight. The same dose is recommended in the Solomon Islands. Ivermectin is available in 3mg tablets.

## Topical 5% permethrin cream (Lyclear®)

Topical 5% permethrin (Lyclear ®) cream for scabies is supplied in a 30g tube. The cream is applied all over the body including from neck to toe and washed off after a minimum of 8 hrs. For children aged 2 months or less permethrin should be washed off after 4 hours.

#### **5.2** Legal status of drug

Permethrin is licenced in the UK for the treatment of scabies. It is listed as on the essential medicines list for the Solomon Islands and recommended as a potential treatment for scabies.

Ivermectin is not licenced for the treatment of scabies in the UK although NICE has provided guidance on its use (https://www.nice.org.uk/advice/esuom29/resources/ivermectin-for-difficulttotreat- scabies-17546902981). Ivermectin is widely used in control programmes for both Onchocerciasis and Lymphatic Filariasis. Ivermectin is listed as on the essential medicines list for the Solomon Islands and recommended as a potential treatment for scabies.

#### **5.4** Drug Storage and Supply

Medications will arrive by plane and will reach the islands by boat at the provincial pharmacy / medical store. The order request will be checked with the supplies delivered. The delivery notice number, delivery date and the medications batch number will be recorded in a log book. Medications

will be taken out of the pharmacy in bulk by the study teams for dispensing in the community. Study teams will maintain a log of all medicines dispensed that can be cross-checked against participants

study records.

WEIGHT	IVERMECTIN TABLETS
	(3mg Tabs)
<15KG	PERMETHRIN
	CREAM
15KG	1
25 – 37.5 KG	2
37.5 – 50 KG	3

## **5.5** Preparation and labelling of IMP

For participants receiving ivermectin, the dose will be determined according to body weight and treatment will be administered under direct supervision of the study team. Drug administration will be recorded in a standardized record form.

Participants assigned to permethrin (due to contra-indication to ivermectin) will receive a tube of cream and will be asked apply the cream from neck to toes before they leave the clinic and under supervision of a study nurse, and leave it on for a minimum of 8 hours, maximum 24 hours if possible. For children aged 2 months or less, cream will applied for a maximum of 4 hours.

#### **5.6** Dosage schedules/modifications

In line with standard treatment the dosing of Ivermectin will use the following weight bands

Permethrin will be used instead of Ivermecitn in the following circumstances

- Pregnancy
- Breastfeeding
- Child <6 months age
- Child <15kg

Where permethrin is indicated the following standard dosing protocol will be used:

- Full tube for adults.
- Half tube for children.
- Apply to whole body and leave on for 1 day before washing off

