#### **Eligibility Criteria:**

All residents of the Atoifi Hospital campus will be invited to participate in the study.

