## **5.9** Trial restrictions

There are no trial restrictions.

As noted above pregnant and breast feeding women and children <15kg will be offered permethrin rather than ivermectin but will still be allowed to participate in the study.

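### Section 5.6 tells every permethrin recipient to leave the cream on for 1 day and omits the 4-hour limit for infants up to 2 months old that the protocol sets elsewhere (minor)

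*Combined protocol and SAP*

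**What the plan says.** Section 5.6 lists who receives permethrin instead of ivermectin: pregnant women, breastfeeding women, children under 15 kg and, as a separate line, "Child <6 months age". It then introduces the dosing without reservation: "Where permethrin is indicated the following standard dosing protocol will be used". Three bullets follow. Two set the amount (a full tube for adults, half for children). The third sets the duration for everyone: "Apply to whole body and leave on for 1 day before washing off".

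Two other places give a different duration for the youngest infants. The permethrin description under section 5.1 says: "For children aged 2 months or less permethrin should be washed off after 4 hours". Section 5.5, which describes supervised application in the clinic, says: "For children aged 2 months or less, cream will applied for a maximum of 4 hours". For other recipients, section 5.5 tells them to "leave it on for a minimum of 8 hours, maximum 24 hours if possible".

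Infants of this age are not screened out. The eligibility criteria in section 3 state: "All residents of the Atoifi Hospital campus will be invited to participate in the study". Section 5.9 adds that "children <15kg will be offered permethrin rather than ivermectin but will still be allowed to participate in the study".

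**The concern.** Section 5.6 is headed as the place for dosage schedules and modifications, so it is where staff would look for an age adjustment. It already makes one, the half tube for children, and a reader could reasonably take its adjustments for children as complete. It does not refer back to 5.5 or to the product description.

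What is at stake is a handling instruction for very young infants. A nurse supervises application, but washing off happens hours later. Section 5.10 assesses compliance at distribution, and no check on removal is described. The contact time therefore depends on what the carer is told. Section 6.3.1 limits safety data to serious events and SUSARs, so a mild reaction to over-long contact would not be recorded.

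**Working it through.** The plan gives no calculated figure to reproduce. The check is a comparison of instructions, with one ratio.

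**Instructions for an infant aged 2 months or less**

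| Place | Applies to this infant? | Contact time |
|---|---|---|
| 5.1, permethrin description | Yes, named by age | wash off after 4 h |
| 5.5 | Yes, named by age | at most 4 h |
| 5.6 | Yes, through the lines for under 6 months and under 15 kg | 1 day |

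The first two agree. The third cannot be followed together with them.

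**Instructions for everyone else.** Section 5.5 allows 8 to 24 h and 5.6 says 1 day. Read as 24 h, 1 day falls at the top of that range, so there is no conflict for older recipients.

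**Size of the excess, per application**

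- 1 day read as 24 h: 24 / 4 = 6 times the limit, and 24 − 4 = 20 h over.
- 1 day read loosely, down to the 8 h minimum that 5.5 gives for general use: 8 / 4 = 2 times the limit, and 8 − 4 = 4 h over.

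The limit is exceeded on either reading. The 6-fold figure is the upper end.

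**How many infants.** The documents give no age distribution, so this part is an assumption used only to judge scale. The study summary expects about 150 people to be treated. Applying the 80% enrolment from section 8 gives a lower figure of 150 × 0.80 = 120. With an assumed 20 to 40 births per 1000 people per year:

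- low: 120 × 0.020 × 2/12 = 0.4 infants
- high: 150 × 0.040 × 2/12 = 1.0 infant

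The population is hospital staff and their families on one campus, so a general birth-rate range may not fit. The result supports few if any, and nothing more precise. The contradiction does not depend on it.

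**After correction.** With the exception added to 5.6, all three places give at most 4 h, and the ratio to the limit falls to 4 / 4 = 1.

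**The case against.** The best defence is that the protocol should be read as a whole. A general rule in 5.6 and a specific age rule in 5.5 are normally reconciled by letting the specific rule govern. Section 5.5 comes immediately before 5.6 and is the operational text: it says what participants are asked to do, under a nurse's supervision, before they leave the clinic. Nothing in the documents says 5.6 would be used on its own. Much of this stands, and it is why the point is minor. It does not remove the contradiction, because 5.6 claims to apply wherever permethrin is indicated and names young infants among the recipients.

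A second defence is damage from text extraction. The ivermectin weight table is split around this section and 5.7 begins mid-sentence. The permethrin list itself reads as complete, so this is only a modest caution.

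A third is that only 5.5 uses the language of a maximum, while the 5.1 description says when the cream should be washed off. That is fair, but both give 4 hours.

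On the other side, a reader might infer that the plan intends a six-fold overexposure of infants. The documents do not support that. The 4-hour limit is stated twice, and what 5.6 lacks is an exception. A reader might also infer likely clinical harm. The documents state no consequence of longer contact in infants, and section 5.7 describes systemic reactions to permethrin as not common.

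**Conclusion.** The concern holds as a minor internal inconsistency. Followed literally, 5.6 gives the wrong wash-off time for infants aged 2 months or less: up to 24 h against the protocol's 4 h, taking 1 day as 24 h. The claim is limited to a possible breach of the protocol's own limit by someone relying on 5.6 alone. Few if any participants are likely to be affected; that judgement rests on the small campus population and an assumed birth rate.

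A reader might also infer that the error reaches the trial's results. It does not. The change in head lice prevalence, the sample size assumptions and the analysis do not depend on how long infants keep the cream on their skin.

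**What to change.** Keep the third permethrin bullet in 5.6 as it stands and add to it: *except infants up to 2 months of age: wash off after 4 hours at most (see 5.5)*. Have the nurse tell the carer this wash-off time when the cream is applied.

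The change should stop there. The treated area and the general contact time are worded differently in 5.5 and 5.6, but this point gives no reason to alter either for other recipients.

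The cost is one added clause and one spoken instruction. Design, sample size, visits and data collection stay the same.

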5.7 Known drug reactions and interaction with other therapies

50-75 KG	4
>75 KG	5

campaigns where >100 million doses have been administered. The most commonly reported side effects are for Ivermectin are headache, dizziness, itch. Adverse events are normally mild and self-limiting with no specific therapy required. Permethrin does not commonly cause any systemic adverse commons.

# **5.8** Concomitant medication

Individuals receiving Warfarin may not receive treatment with Ivermectin due to potential interactions. No individuals outside of the capital of the Solomon Islands (Honiara) are receiving Warfarin due to a lack of INR monitoring facilities and therefore it is not anticipated that any individuals in the study will be receiving a contra-indicated concomitant medication. Permethrin will be offered if a patient taking warfarin was identified.

## **5.9** Trial restrictions

There are no trial restrictions.

As noted above pregnant and breast feeding women and children <15kg will be offered permethrin rather than ivermectin but will still be allowed to participate in the study.

## **5.10** Assessment of compliance

Drugs will be delivered as a single observed treatment and therefore compliance will be assessed at the time of drug distribution.

# 6. SAFETY REPORTING FOR DRUG TRIALS

#### 6.1 **DEFINITIONS**

Term	Definition
Adverse Event (AE)	Any untoward medical occurrence in a participant to whom a medicinal product has been administered, including occurrences which are not necessarily caused by or related to that product.
	An AE can therefore be any unfavourable and unintended sign (including an abnormal laboratory finding), symptom, or disease temporally associated with the use of an investigational medicinal product (IMP), whether or not considered related to the IMP.
Adverse Reaction (AR)	Any untoward and unintended response in a participant to an investigational medicinal product which is related to any dose administered to that participant.
	The phrase "response to an investigational medicinal product" means that a causal relationship between a trial medication and an AE is at least a reasonable possibility, i.e. the relationship cannot be ruled out.
	All cases judged by either the reporting medically qualified professional or the Sponsor as having a reasonable suspected causal relationship to the trial medication qualify as adverse reactions.
Serious Adverse Event (SAE)	

A serious adverse event is any untoward medical occurrence that:

Results in death

Is life-threatening

	
 
Requires inpatient hospitalisation or prolongation of existing hospitalisation
 
Results in persistent or significant disability/incapacity
 
Consists of a congenital anomaly or birth defect
 

	Other 'important medical events' may also be considered serious if they jeopardise the participant or require an intervention to prevent one of the above consequences.
Serious Adverse Reaction (SAR)	An adverse event that is both serious and, in the opinion of the reporting investigator, believed with reasonable probability to be due to one of the trial treatments, based on the information provided.
Suspected Unexpected Serious Adverse	A serious adverse reaction, the nature and severity of which is not consistent with the information about the medicinal product in question set out:
Reaction (SUSAR)	
 
In the case of a product with a marketing authorisation, in the summary of product characteristics (SmPC) for that product
 
In the case of any other investigational medicinal product, in the investigator
 

L	brochure (IB) relating to the trial in question.

#### 6.2 CAUSALITY

Most adverse events and adverse drug reactions that occur in this study, whether they are serious or not, will be expected treatment-related side effects due to the drugs used in this study. The assignment of causality should be made by the investigator responsible for the care of the participant using the definitions in the table below.

If any doubt about the causality exists the local investigator should inform the study coordination centre who will notify the Chief Investigators. The pharmaceutical companies and/or other clinicians may be asked to advise in some cases.

In the case of discrepant views on causality between the investigator and others, all parties will discuss the case. In the event that no agreement is made, both points of view are to be reported.

Relationship	Description
Unrelated	There is no evidence of any causal relationship
Unlikely	There is little evidence to suggest there is a causal relationship (e.g. the event did not occur within a reasonable time after administration of the trial medication). There is another reasonable explanation for the event (e.g. the participant's clinical condition, other concomitant treatment).
Possible	There is some evidence to suggest a causal relationship (e.g. because the event occurs within a reasonable time after administration of the trial medication). However, the influence of other factors may have contributed to the event (e.g. the participant's clinical condition, other concomitant treatments).
Probable	There is evidence to suggest a causal relationship and the influence of other factors is unlikely.
Definitely	There is clear evidence to suggest a causal relationship and other possible contributing factors can be ruled out.
Not assessable	There is insufficient or incomplete evidence to make a clinical judgement of the causal relationship.

#### 6.3 **REPORTING PROCEDURES**

Depending on the nature of the event the reporting procedures below should be followed. Any questions concerning adverse event reporting should be directed to the study coordination centre in the first instance.

#### 6.3.1 Non serious Adverse Reactions (ARs)/Adverse Events (AEs)

Given the established safety profile of the drugs being used in this study and the fact that they are being used for established indications we will only collect data on SAEs and SUSARs.

#### 6.3.2 Serious Adverse Reactions (SARs)/Serious Adverse Events (SAEs)

Serious Adverse Events (SAEs) and Serious Adverse Reactions (SARs) should be reported to the study coordination centre within 24 hours of the local site being made aware of the event.

An SAE form should be completed and submitted to the study coordination centre with as much detail of the event that is available at that time. If awaiting further details, a follow up SAE report should be submitted promptly upon receipt of any outstanding information. The CI (for a single-centre trial) or PI (for a multi-centre trial) must record the event with an assessment of seriousness, causality and expectedness.

Any events relating to a pre-existing condition or any planned hospitalisations for elective treatment of a pre-existing condition do not need reporting as SAEs.

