#### 6.3.3 SUSARs

All SAEs assigned by the PI or delegate as both suspected to be related to IMP-treatment and unexpected will be classified as SUSARs and will be subject to expedited reporting to the Regulatory Authority, in the UK: Medicines and Healthcare Products Regulatory Agency (MHRA). The Sponsor (or delegate) will inform the MHRA, and the ethics committee of UK-relevant SUSARs within the required expedited reporting timescales (as per LSHTM Standard Operating Procedure for recording, managing and reporting of adverse events for IMP studies).

For blinded trials, all SUSARs must be reported assuming the active compound is involved.

In the case of a suspected, unexpected, serious adverse reactions (SUSAR), the staff at the site should:IVM-LICEPage 17 of 26Version 1.0 16/05/17

- 1. Contact the study coordination centre immediately by phone or email to inform them of the event.
- 2. Submit a completed SAE form (signed and dated) within 24 hours, together with relevant treatment forms and anonymised copies of all relevant investigations.
- 3. Submit any additional information promptly upon request.

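### The SAE reporting exemption in section 6.3.2 covers any event linked to a pre-existing condition, so serious worsening after treatment need not be reported and may be recorded nowhere

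*Combined protocol and SAP*

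**What the plan says.** Section 6.1 defines the terms. It reads "A serious adverse event is any untoward medical occurrence that" and then lists the seriousness criteria, among them death, danger to life, and "Requires inpatient hospitalisation or prolongation of existing hospitalisation". The definition of an adverse event in the same table is independent of cause, "including occurrences which are not necessarily caused by or related to that product".

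Section 6.3.2 sets the duty. SAEs and SARs "should be reported to the study coordination centre within 24 hours of the local site being made aware of the event", and the responsible investigator must assess each one for seriousness, causality and expectedness. The section then closes with the exemption: "Any events relating to a pre-existing condition or any planned hospitalisations for elective treatment of a pre-existing condition do not need reporting as SAEs".

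Two neighbouring sections decide what happens to an exempted event. Section 6.3.1 says of the study's safety data that "we will only collect data on SAEs and SUSARs". Section 6.3.3 says "All SAEs assigned by the PI or delegate as both suspected to be related to IMP-treatment and unexpected will be classified as SUSARs".

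**The concern.** The exemption has two limbs joined by an 'or'. The second, planned elective admission, is a conventional carve-out and is not in dispute. The first releases every event with a link to a condition the participant already had. It does not require the condition to be stable or the event to be minor, and it does not ask whether treatment could have contributed.

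This matters because little else would pick up what the rule lets go. Non-serious events are deliberately not collected, so serious-event reporting is the study's only planned safety record. A site that follows the sentence as written could leave out a serious deterioration after dosing, and nobody would then grade its relation to treatment or whether it was expected.

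**Working it through.** No arithmetic applies. The check sets the safety provisions side by side and follows one event through them.

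**Test event.** A participant with a known chronic illness takes the study treatment. Some days later the illness worsens and leads to an emergency admission.

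1. *Definition (6.1).* The admission is an untoward occurrence that meets the hospitalisation criterion, so it is an SAE. Nothing in 6.1 excepts pre-existing illness. Attributing the event to that illness does not take it out of the definition, which covers unrelated events too.
2. *Duty (6.3.2, opening).* As an SAE it is reportable within 24 hours and must be assessed.
3. *Exemption (6.3.2, last sentence).* It relates to a pre-existing condition, so it need not be reported as an SAE. A death by the same route is treated the same way.
4. *Other data collection (6.3.1).* Only SAEs and SUSARs are collected. No lower category exists in which the event would still be logged.
5. *SUSAR route (6.3.3).* SUSARs are selected from SAEs. An event not handled as an SAE has no clear way in.
6. *Causality scheme (6.2).* The table uses the participant's clinical condition as a factor to weigh when grading an event as unlikely or possible. The protocol thus means underlying illness to be judged within the assessment, whereas the exemption allows the event to be set aside before any assessment.
7. *Other safeguards.* Section 9.1 provides passive monitoring only. Section 9.3 mentions review of adverse event forms at later visits but adds no category of event to be collected. Section 11 appoints no DSMB. None of these restores reporting of worsening.

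**Can 'pre-existing' be verified?** The Data Collection text in section 7 names scabies, impetigo and headlice as the baseline items. The Duration text in section 3 mentions a baseline medical assessment, but no medical-history item is listed. The documents therefore show no record against which a claim that a condition was pre-existing could be checked. The three named conditions are themselves pre-existing when found at baseline, so a serious complication of scabies or impetigo also falls under the literal wording.

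**Does the population make this relevant?** Section 4.1 offers treatment to everyone whether or not they have signs of disease. Section 4.3 excludes people unwell on the dosing day, and the exclusion criteria in section 3 remove those with a contra-indication. Neither removes people with stable chronic illness. How many such people there are is not stated.

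**The case against.** The strongest reply is that the sentence permits and does not forbid: a site may still report. It also names only SAEs, while 6.3.2 places the 24-hour duty on SARs as well, and 6.1 defines a SAR as a serious event believed with reasonable probability to be due to treatment. Section 6.3.3 separately tells sites to contact the coordination centre at once about a suspected SUSAR. On that reading, worsening attributed to the drug is still caught, and mainly worsening judged unrelated is released. Much of this stands. A reader might infer that serious worsening would certainly go unrecorded, and the text does not support that. The reply does not close the gap, however. A SAR is also an SAE, and no provision says that the SAR or SUSAR duty prevails over the exemption.

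It is also fair to say that 6.3.2 narrows a duty and does not redefine an SAE. The definition in 6.1 remains intact. The conflict is between that definition, with the reporting duty built on it, and the release at the end of 6.3.2.

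A reader might further infer that section 6.2 makes matters worse by saying "Most adverse events and adverse drug reactions that occur in this study, whether they are serious or not, will be expected treatment-related side effects", as if that stopped events becoming SUSARs. It does not. The sentence is a forecast about most events. Section 6.1 fixes expectedness by reference to the product information, and 6.3.2 already requires expectedness to be assessed for each reported event.

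Finally, safety is neither an objective nor an outcome, and the protocol justifies limited collection by the established profiles of the drugs. That lowers the stakes. But 6.3.1 already uses that argument to drop non-serious events, which leaves serious-event capture as the only safety record.

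**Conclusion.** The point holds as a defect in a stated rule. Followed as written, the first limb of the exemption releases from reporting events that meet the protocol's own SAE definition, including fatal ones. Those events may then be recorded nowhere and may miss the causality and expectedness assessment. How far the SAR and SUSAR duties would recover them is unresolved in the text.

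No numerical size can be given. The documents state neither the frequency of chronic illness on the campus nor an expected number of SAEs, so a missed-event rate would rest on an invented count. The denominator is also open: the study summary expects about 150 people to be treated, while the sample-size text lists 80% enrolment without saying whether 150 is before or after it. It would be wrong to infer that the headlice result is at risk, since the exemption does not touch the measurement or analysis of prevalence.

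The conclusion assumes that site staff apply the sentence literally and that some participants have a pre-existing condition. The second is plausible from the broad eligibility but is not documented, apart from the skin conditions and headlice that the study itself looks for. The wording should be corrected because serious-event reporting is the study's only safety data and the correction is cheap.

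**What to change.** In section 6.3.2, restrict the exemption to hospitalisations planned before enrolment for a pre-existing condition that has not worsened. Add that any new or worsened event meeting a seriousness criterion in 6.1 is reported as an SAE, even where it relates to a pre-existing condition. That brings 6.1, 6.3.1, 6.3.2 and 6.3.3 into line and removes the doubt about which duty prevails. Section 6.2 needs no change for this purpose.

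The cost is a sentence or two of protocol wording and possibly a few more SAE forms. Treatment, visits, sample size and the headlice analysis stay as they are.
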